### 13.2.2 Reporting of Serious Adverse Events

All SAEs must be reported in the format detailed by the Serious Adverse Event Report Form to the SCOPE International Pharmacovigilance by email or fax within 24 hours of the Investigator becoming first knowledge (Note: If local regulations require shorter reporting timelines, the stricter requirement will apply).

**SAEs must be reported within 24h to**

**email: [[contact]](mailto:[contact]) or**

**[contact]**

Any information not available at the time of the initial SAE report (e.g. an end date for the AE or laboratory values received after the report) must be documented on a SAE report form, with the box "Follow-up" indicated under "Report type". AEs initially reported as non-serious but later assessed as serious, must be forwarded immediately to SCOPE International Pharmacovigilance on a SAE report form.

SCOPE on behalf of the Sponsor will notify the competent authorities, IECs/IRBs and all Investigators of any suspected SARs that are unexpected (SUSARs) and other significant safety issues in line with applicable legal requirements.

All reporting of adverse events must strictly adhere to relevant data protection regulations to ensure patient confidentiality.

### 13.3 Period of Observation

For the purposes of this study, the observation period for collecting of AEs extends from the time the patient provides informed consent until the last patient visit. AEs occurring prior to Visit 1 (screening) should be recorded as part of the patient's medical history and will not require separate reporting. This approach streamlines the reporting process and ensures that only relevant AEs occurring during the study period are documented.

Any serious AE occurring during this study must be monitored beyond the observation period until:

- It has been shown to be unrelated to the Investigational Medicinal Product (IMP) or placebo
- The event has resolved

- There has been improvement or no further improvement is expected, and the case has been fully explained and assessed.

Medical conditions diagnosed at the screening visit will only be documented as AEs, if they are known to have started or are suspected to have started after the ICF has been signed. All other medical findings during examinations at the screening visit will be documented as medical history. Medical judgment should be exercised to estimate if a condition likely began between the signing of the informed consent and the date/time of the medical examination. Adverse Events will be followed up throughout the course of the clinical trial, in compliance with ICH GCP guidelines and local regulatory requirements.

### **13.4 Potential Risks and Potential Adverse Events**

The risk to patients in this trial will be minimized by compliance with inclusion/exclusion criteria, close clinical and imaging monitoring during the study, assessment of the nature, frequency, and severity of adverse events, avoidance of prohibited treatments and adherence to Investigator guidance. In addition, guidelines for managing severe allergic reactions are provided in the Appendix 24.2. Detailed criteria for study discontinuation are given in section 9.3 and post-treatment observational periods defined in sections 10.2.3 and 14.5. Furthermore, safety will be closely monitored on an ongoing basis by a Data and Safety Monitoring Board (DSMB) as outlined in section 19.1.3.

#### **13.4.1 Risks of Blood Drawing**

Adverse events associated with drawing blood for RBC donation include vasovagal syncope with needle insertion and in rare cases hypotension secondary to volume depletion. Exclusion of patients with a history of cardiovascular disease further reduces the risk of this complication. Infection is a potential risk but is unlikely due to the closed system and the maintenance of sterile technique. Clinically significant iron deficiency and anemia may occur as a consequence of the blood donation.

#### **13.4.2 Risks of Leukapheresis**

Possible risks comprise hematoma at the puncture site, an infection due to venous puncture (the tubing system for the withdrawal is a sterile one-way system), prickling paresthesia due to anti-coagulating agents, which are added during the centrifugation of the blood. Further, break into a sweat, nausea, vomiting or hypotension and faint as expression of vasovagal response can occur. Exclusion criteria for leukapheresis: pregnancy and difficult peripheral venous access.

#### **13.4.3 Risks of Lumbar Puncture**

Effusions, stiffness, irritation of the tissue due to the injection, post-puncture headache, in very rare cases post-puncture infection. Headaches or irritation of a nerve root can occur but are rare (headaches) or very rare (nerve root irritation, hematoma).

#### **13.4.4 Risks of MRI**

Gadolinium is used as a contrast agent with MRI approved by the Swissmedic and European Medicines Agency (EMA). No serious side effects have been associated with its use. Approximately 5 to 10 percent of patients develop transient headaches following administration, but it is not clear whether the headaches are associated with the drug. The effect of gadolinium on the developing fetus remains partly unknown. Animal studies have shown a delay in development but no developmental abnormalities. Consequently, women of childbearing potential will be entered into this study only if an effective means of birth control is in use. A pregnancy test will be done prior to beginning the study and at each follow-up visit. The risk of nephrogenic systemic fibrosis is increased in patients with profoundly impaired renal function (glomerular filtration rate <30mL/minute).

### 13.4.5 Risks of Therapy

The tolerance protocol that is proposed here has been extensively used in rodents for many years, with no major safety issues arising. For a complete summary of safety information, refer to the Investigator's Brochure. From the extensive experience with peptide-coupled cells we do not expect any significant hematopoietic or organ toxicity in humans. Data from two phase I trials with myelin peptide-coupled cells in MS patients are consistent with this assumption and did not reveal any signs of toxicity in any of the nineteen patients who have been treated [57]; ETIMSred Trial unpublished).

**Aggregates:** The formation of aggregates is a major concern in cell-based therapies. Aggregates might cause thromboembolic events, particularly in the lungs after intravenous infusion, but also other venous and arterial vascular compartments. The peptide-coupling procedure induces changes in the deformability of RBCs and the surface of the membrane, which might cause thromboembolism. Pre-clinical studies did not reveal any thromboembolic events following single or repeated administrations of peptide-coupled RBCs. In line with preclinical experience two prior studies in MS patients using either PBMCs coupled with seven myelin peptides or RBCs coupled with seven myelin peptides were tolerated well in MS patients. The following measures were taken to reduce the risk of embolism: 1) formation of aggregates will be carefully checked and excluded in every product prior to release and infusion, and 2) peptide-coupled RBCs as well as uncoupled RBCs will pass through a 40 µm filter in a standard blood transfusion kit. Appropriate monitoring of patients during and after infusion is mandatory to ensure appropriate medical care.

**Hypersensitivity and cytokine response:** In pre-clinical experiments and two phase I trials (Lutterotti et al., 2013; ETIMSred Trial unpublished) the i.v. use of peptide-coupled cells did not show any risk of anaphylaxis. Cytokine response to the drug product has not been observed in animals, and our in vitro data in human cells did not reveal any cytokine response. Patients will be monitored to provide immediate adequate medical measures in case anaphylaxis should occur (see section 14.5). In case of severe allergic (anaphylactic) reactions, standardized medical treatment should be applied. An example for an emergency treatment is given in the Appendix 24.2.

Risk of a transfusion reaction will be mitigated by thorough tracking of the autologous blood product.

**Immune activation and disease exacerbation:** The aim of the therapy is the downregulation of an autoreactive immune response through the induction of immune tolerance. However, the induction of an immune response leading to exacerbation of disease cannot be fully excluded. The type of trial, which is based on using MRI measures of inflammation as a sensitive safety measure, is considered optimal in this regard, and clear rules triggering safety data review by a DSMB (see section 19.1.3) have been defined to minimize risks and enable medical actions at the earliest possible time point.

**Risk of infection:** Some biologic and non-biologic therapies for the treatment of MS have been associated with an increased risk of infection. As a measure of precaution, the Investigator or study physicians are required to carefully monitor for any signs or symptoms of infection (see section 14.5).

**Carcinogenicity:** Peptide-coupled RBCs are mature autologous cell populations and do not have a cell nucleus and thus do not have the ability to proliferate. It has not been described that MS patients have increased risks to develop tumors [58].

[REDACTED]

**Reproductive and developmental toxicity:** Reproductive and developmental toxicity was not assessed in pre-clinical studies. Available data do not suggest any reproductive or developmental toxicity or influence on reproductive performance to arise from the single injection of autologous

cells. Nevertheless, the patients will be informed about the remote potential of such risks and will have to sign an informed consent that they have to use acceptable methods of contraception.

**Injection site reactions:** Peptide-coupled RBCs will be administered by IV infusion. The medication will be released slowly as a drip from a bag and into a tube that is attached to the needle. It is common for a patient to experience reactions at the injection site as a side effect of the venous puncture. Common skin reactions include redness, bruising, pain, or swelling. These symptoms usually resolve on their own within a short period. Slowing of the infusion rate may be necessary in the event of an infusion reaction.

#### 13.4.6 Risks of Manufacturing and Transportation

The IMP/placebo will be manufactured, tested, and released in compliance with GMP requirements including appropriate sterility testing. Nonetheless, there is still a risk that manufacturing of the IMP/placebo will have to be stopped or that the final product will not be conforming to specifications and can be not released for use. Despite all due care, there is a certain risk of the possible transmission of germ components. Furthermore, there is also the risk of damage to the starting product or the final product due to incorrect handling or exceeding of the expiry date e.g. due to prolonged transport times so that the starting product can no longer be used for manufacturing, or the final product can no longer be used for infusion. In these cases, study treatment cannot be carried out as scheduled. The management of positive sterility test results during manufacturing and after administration of IMP to a patient is illustrated in Appendix 24.7.

There is also a minor risk of mixing up patient blood and IMP/placebo. Safety measures have been taken to minimise the risk and to ensure that the patient will receive the own IMP/placebo. This also includes serological crossmatch or bedside testing immediately prior to each infusion according to the local regulations. In case of incompatibility the IMP/placebo will not be infused.

If study treatment cannot be carried out as scheduled, the patient will stay on study and receive his/her next treatment according to the study schedule.

### 13.5 Pregnancies

Female patients should take all appropriate precautions to avoid becoming pregnant during this study. As such, women of childbearing potential should use adequate contraception throughout the trial, including the treatment phase and for 4 weeks after the last dose of CLS12311. Regular pregnancy tests will be performed during the study. Patients who become pregnant at any time during the study will be instructed to immediately inform the investigator and come in for an unscheduled visit. A positive pregnancy test must be confirmed by a urine pregnancy test at the central laboratory.

The Investigator has to document any pregnancy occurring in a female patient after the first study dose until patient's last study visit on the Pregnancy Report Form and submit to the Sponsor's designee immediately (i.e. no more than 24 hours after learning of the pregnancy), either by faxing or by emailing:

**SCOPE International Pharmacovigilance**

**email:** [[contact]](mailto:[contact])

**[contact]

Pregnant patients who received at least one dose of CLS12311 and prematurely discontinue the study prior to the last scheduled visit have to perform the early discontinuation (ED) visit (see section 12.1.9), except for the MRI examination and pregnancy testing.

After the birth, the investigator will contact the patient, who become pregnant to obtain data on pregnancy outcomes. The Investigator has to email or fax the Pregnancy Report Form to SCOPE International Pharmacovigilance when updated information on the course and outcome of the pregnancy becomes available. In addition, patients may volunteer further information regarding child health at 12 months after birth using the validated infant health questionnaire (ASQ-3). After

a pregnancy has been confirmed, an informed consent will be sought regarding collecting information on the health and well-being of the infant.

Pregnancy per se does not classify as an AE. However, any AEs related to a pregnancy have to be reported like any other AEs in eCRF Adverse Event page. SAEs related to pregnancy and any abnormal outcome (i.e. congenital anomalies, spontaneous abortion or fetus death, adverse reactions in the neonate that are classified as serious) have to be reported on the SAE Report Form within 24 hours to SCOPE PV and documented in the eCRF Adverse Event page.

### 13.6 Ongoing Safety Assessment

An external, independent Data and Safety Monitoring Board (DSMB) will review safety data throughout the study as outlined in section 19.1.3.

## 14 VISIT SCHEDULE AND ASSESSMENTS

### 14.1 Procedures at Each Visit

#### 14.1.1 Baseline

Baseline evaluations and data collection will be used to determine eligibility for enrollment and to document patient clinical status prior to treatment. Information to be collected includes:

- Date of informed consent
- Demography
- Tobacco use
- Height and weight
- MS history (date of first MS symptom, date of first MS diagnosis, prior relapses, prior disease modifying therapies and symptomatic therapies)
- SARS-CoV-2 vaccination status
- Medical history (except MS history)
- Current medication except for MS (taken regularly for chronic conditions, or within the past 30 days)
- Physical examination
- Vital signs
- ECG (at least a 6-lead)
- Childbearing potential and ask patient if she is pregnant (pregnancy is an exclusion criterion)
- Urinary pregnancy test
- Central labs: Infectious Disease Screen (no extra blood sample needed)
- Hematology: complete blood count with differential and platelet count, Coombs test, coagulation studies (PT, PTT, INR) and sedimentation rate, blood group
- Clinical chemistry: Sodium, potassium, creatinine, eGFR, urea, total bilirubin, GGT, ALT/GPT, AST/GOT, alkaline phosphatase, total protein, albumin, lactate dehydrogenase, fibrinogen, CRP, iron, ferritin, haptoglobin, eGFR
- Urinalysis: specific gravity, pH, glucose, protein, ketones, nitrite, leukocytes and blood

- HLA typing HLA- [REDACTED] alleles (no extra blood sample needed; will be taken from blood collected for antigen specificity testing)
- Antigen specificity: collect 30 ml of EDTA blood
- Biomarker: collect one serum tube (5 ml)
- **Cranial MRI (contrast enhanced)**; (can be performed within 5 days after V1, latest on the same day prior to the blood donation)
- EDSS
- 9-HPT
- T25-FW
- SDMT
- Adverse events
- Assessment of inclusion/exclusion criteria

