 A telephone interview will be conducted 3-5 days after the second dose of the first treatment cycle has been administered.

 The exact time point of V2 is not specified as it is based on central allocation to the dose group and depending on patient recruitment. Other assessments at the study site may be performed on the day before the blood donation

 Central labs: At visit 1 serology testing (Anti-HIV-1/2, HBsAg, Anti-HBc, Anti-HCV, screening for syphilis from biochemistry blood to check patient eligibility for blood donation)

 is carried out on the following working day. If the phone consultation of the [REDACTED] coincides with the phone visit [REDACTED], the phone consultation of the [REDACTED] will be skipped.

 For Sentinel Patients, no blood donation will be performed at [REDACTED]. Only safety-related assessments will be conducted.

 Sentinel Patients are not required to attend [REDACTED] and [REDACTED], as no IMP will be administered. Instead, sites will perform telephone-based AE assessments. Optional onsite visits may be arranged upon patient request.

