**Figure 7-1    Patients’ enrollment and safety assessments in the treatment phase**

## 7.2 Safety Follow Up Phase: approx. 31 weeks

At the completion of the treatment phase, patients will enter a 31-week safety follow up (SFU) period, including three visits: three weeks after the end of the treatment period (Week 20), at Week 24 and at Week 48.

During the SFU, patients will be assessed at clinical visits as per Schedule of Events – please refer to Table 4.1 for further details.

The DSMB will reconvene after the completion of [REDACTED] to assess the safety outcomes of the trial.

[figure not shown]
If patients wish to discontinue the unblinded SFU and the last visit has been more than 8 weeks ago, they should be invited for an ED visit to capture safety data and ensure continued patient monitoring.

As the duration of the treatment effect is not known, patients may begin another DMT during the SFU, at the discretion of the investigator. However, every effort should be made to have patients complete the SFU and all related assessments, regardless of whether or not they receive alternative treatment for their MS.

In summary, this Phase Ib trial is designed to provide a maximum of safety throughout both single dose escalation and second treatment cycle.

Safety data will be evaluated by a DSMB after key milestones to assess the overall safety of CLS12311 and the different dose levels tested. A brief overview of the course of the Phase Ib study is shown in Figure 7-2.

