2.3 Overall Study Design

Open-label, ascending-dose Phase Ib trial to evaluate the safety and tolerability of three doses of CLS12311 in patients with relapsing-remitting multiple sclerosis (RRMS).

The study will be conducted at approximately 12 sites in Europe.

The total duration will be at least 48 weeks for each participant and will include a total of 16 visits divided into two phases: an open-label treatment phase and a safety follow-up phase. The study phases are described in more detail in the following paragraphs.

Patient eligibility will be assessed during Visit 1 (week 0) at baseline, where general patient and disease characteristics will be recorded. Patients who meet the criteria for enrollment will be sequentially allocated to one of the dose groups. The allocation to the dose group and the timing of treatment administration will be centrally coordinated to ensure appropriate safety assessments between dosing of patients. Hence, the time-period between Visit 1 and Visit 2 might vary between patients.

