4.7 Definition of Baseline Value

The baseline value for a variable is defined as the last non-missing value collected before the first blood donation.

More details on the definition of baseline can be found in Section 5.

Absolute change from baseline will be calculated as

$$\text{Absolute Change from Baseline at Visit } X = \text{Value at Visit } X - \text{Baseline Value}$$

Relative change from baseline (%) will be calculated as

$$\text{Relative Change from Baseline at Visit } X = \frac{\text{Value at Visit } X - \text{Baseline Value}}{\text{Baseline Value}} \times 100$$

Note: Patients with a baseline value of ‘0’ will be excluded from the calculation of relative change.

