4.8 Visit Windows

No visit windowing will be performed. All data will be analyzed using the nominal visit number

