5.5.3 Magnetic Resonance Imaging

Cranial MRI will be performed as follows; the data will be collected in the eCRF as described below:

	■	■	■	■	■
Number of contrasts enhancing lesions (CEL)	x	x	x		
Number of new/enlarging T2 lesions*		x	x	x	x
Total number of T2 lesions	x				

* New/enlarging T2 lesions are calculated in reference to the previous MRI

Cranial MRI scans without contrast agent can also be performed during unscheduled visits. The number of new/ enlarging T2 lesions observed during unscheduled visit will be documented in the eCRF.

The number of CELs, total or new/ enlarged T2 lesions collected during the scheduled visits will be summarized. All collected data will be listed.

Baseline will be defined as the number of CELs at Visit 1.

Lesion size data will be available from MRI images and will be summarized by visit, dose group, and overall.

When combining the eCRF-based MRI data and the MRI data provided by Jung Diagnostics GmbH (JungD), the following rules will be applied:

- Data collected during an unscheduled visit after a scheduled visit with planned MRI assessments where MRI was not performed will be assigned to that scheduled visit.
- Gad+ lesion data available in the JungD data set will not be used if it is collected during a visit where contrast enhancing lesion (CEL) data collection is not planned.
- Gad+ lesion data available in the JungD data set where CEL data collection was planned and is not available in the eCRF due to data collection issues will be used.

The following statistical output will be presented:

Table 15.2.3 Summary of MRI Data – Modified Safety Analysis Set

The default summary statistics of number of CELs, new/ enlarging T2 and total number of T2 lesions and lesion size as well as change from baseline will be presented by dose group and overall. This summary will be performed by treatment cycle subgroup.

Listing 16.2.5 MRI Data – Enrolled Analysis Set

MRI results will be listed.

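### New/enlarging T2 counts are tabulated by nominal visit without regard to the time between scans, so they are not comparable across visits or patients

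*Protocol*

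**What the plan says.** The number and size of brain lesions belong to the primary safety endpoint (Protocol section 6, SAP 2.2.1).

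- **Reference scan.** SAP 5.5.3: "New/enlarging T2 lesions are calculated in reference to the previous MRI". Each T2 count therefore covers one interval between scans.
- **Summary.** Table 15.2.3 gives default summary statistics of the counts from scheduled visits, by dose group, overall and by treatment-cycle subgroup. SAP 4.8 does no windowing: "All data will be analyzed using the nominal visit number".
- **Baseline scan.** Protocol 14.1.1: it "can be performed within 5 days after V1, latest on the same day prior to the blood donation". For the MRI table, SAP 5.5.3 states "Baseline will be defined as the number of CELs at Visit 1". The general rule in SAP 4.7 takes the "last non-missing value collected before the first blood donation". The readable text plans no second scan before dosing.
- **Wait to donation.** Protocol 4.1, footnote 16: "The exact time point of V2 is not specified as it is based on central allocation to the dose group". SAP 2.3: "the time-period between Visit 1 and Visit 2 might vary between patients".
- **Later scans.** Treatment ends at week 17. Follow-up visits come "three weeks after the end of the treatment period (Week 20), at Week 24 and at Week 48" (Protocol 7.2), with no MRI at the first of these.

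Other accumulating outcomes are adjusted for time. SAP 5.5.2 annualises relapses per subject-year, and SAP 5.5.1 adds exposure-adjusted rates for TEAEs.

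**The concern.** A count of lesions since the last scan grows with the time since the last scan. When the intervals differ by a factor of more than three and only raw counts are shown, a reader scanning Table 15.2.3 from left to right sees rises and falls that come from the visit schedule. The first interval has a further defect: it starts at the baseline scan, not at donation or dosing, so lesions formed while an untreated patient waits for a slot enter the first post-dose count. Two patients with the same disease activity but different waits will show different Visit 7 counts.

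Protocol 13.4.5 relies on MRI inflammation as a sensitive safety measure for disease exacerbation, and the DSMB receives numbers of new lesions. There are nine patients and no control group, so timing within the patient is the main means of judging whether new T2 lesions follow treatment.

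**Working it through.** **Inputs**
- MRI visits: the MRI row of the schedule marks the same columns as the laboratory row, and SAP 5.5.8 names the laboratory visits as 1, 7, 13, 15 and 16.
- Weeks: Visit 1 is week 0, end of treatment (Visit 13) week 17, Visit 15 week 24, Visit 16 week 48. Visit 7 is taken as week 7. This is inferred from the synopsis, which mentions week 7 safety data, because the schedule header is redacted.
- Lesion rate and length of wait: the documents give neither, so both are assumed below.

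**Schedule check.** 17 + 31 = 48 weeks and 17 + 3 = week 20, both as stated.

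**Scan gaps.** Visit 1 to 7: 7 − 0 = 7 weeks, plus any wait. Visit 7 to 13: 17 − 7 = 10. Visit 13 to 15: 24 − 17 = 7. Visit 15 to 16: 48 − 24 = 24.

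**Constant activity, zero wait.** Expected count = rate × gap, so the rate cancels from any ratio. Week 48 against a 7-week interval is 24/7 = 3.4, and against the 10-week interval 24/10 = 2.4. For illustration, expected new T2 lesions per patient (annual rate × gap/52.18):

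| Assumed rate per year | Visit 7 | Visit 13 | Visit 15 | Visit 16 |
|---|---|---|---|---|
| 1 | 0.13 | 0.19 | 0.13 | 0.46 |
| 3 | 0.40 | 0.57 | 0.40 | 1.38 |
| 10 | 1.34 | 1.92 | 1.34 | 4.60 |

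**Adding a wait of w weeks.** If week 7 runs from Visit 2, the first interval is 7 + w. The share before donation is w/(7 + w), and the week 48 to Visit 7 ratio is 24/(7 + w).

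| w (assumed) | First interval | Share before donation | Week 48 / Visit 7 | Pre-donation lesions at 3 per year |
|---|---|---|---|---|
| 0 | 7 | 0% | 3.4 | 0 |
| 4 | 11 | 4/11 = 36% | 24/11 = 2.2 | 0.23 |
| 8 | 15 | 8/15 = 53% | 24/15 = 1.6 | 0.46 |
| 13 | 20 | 13/20 = 65% | 24/20 = 1.2 | 0.75 |

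The two effects pull against each other: a longer wait contaminates the Visit 7 count more, but narrows its contrast with week 48. The ratios of week 48 to Visit 13 (2.4) and to Visit 15 (3.4) do not depend on the wait. Within the Visit 7 column, a patient who waited 13 weeks would be expected to show 20/7 = 2.9 times the count of one who did not wait, at the same activity.

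**Sensitivity.** If only 6 weeks separate donation and Visit 7, the shares become 4/10 = 40%, 8/14 = 57% and 13/19 = 68%.

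**With a rate.** A constant 3 per year would show as 3.0 per year at every visit, instead of 0.40, 0.57, 0.40 and 1.38.

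**The case against.** The study is exploratory, defines no hypotheses and plans no estimate or test of an MRI effect. Contrast-enhancing lesions are counted at three scans and do not accumulate with the gap, so they remain a guide to early worsening. With nine patients, visit dates and MRI results are listed individually. All of this stands and limits the harm. It does not make the T2 rows of the summary table comparable, and visit dates are not scan dates: most scans may fall up to 5 days either side of the visit, and SAP 5.5.3 moves some unscheduled scans to a scheduled visit.

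Four stronger readings are tempting, and the documents do not support them:

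- *The wait is open-ended.* Protocol 10.2.4 places treatment within 13 weeks of enrollment. It also permits postponement, and a 13-week wait before donation would need it. Part of Protocol 14.3 is redacted and may contain a limit. One can say only that the readable text sets no firm maximum.
- *Later dose groups waited longer.* Allocation is sequential, but Protocol 7.1 describes a strict enrollment order whose figure is not available. If enrollment is itself staggered, waits need not differ by group.
- *Natural activity will be reported as a treatment effect.* No such effect is estimated. Nor does every early exacerbation become undetectable, given the contrast-enhancing lesion counts and the relapse assessments.
- *The baseline scan should be moved next to donation.* Protocol 8.1 ties the MRI to the qualification criteria, and 14.1.1 uses baseline evaluations for eligibility. The second clause of the 14.1.1 wording may already allow a scan up to donation day. The SAP was revised after data review, so the trial appears to be past that stage.

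**Conclusion.** The concern holds for new/enlarging T2 lesions. Raw counts by nominal visit are not comparable across visits or between patients, and the Visit 7 count mixes pre-donation with post-donation activity to an extent the table does not show. The 2.4- to 3.4-fold inflation at week 48 holds for any constant lesion rate, but assumes zero wait and Visit 7 at week 7. The 36% to 65% pre-donation share assumes waits of 4 to 13 weeks with week 7 counted from Visit 2; on that timeline the week 48 to Visit 7 ratio falls to between 2.2 and 1.2. Constant activity up to week 48 is itself a simplification, since Protocol 7.2 lets patients start another disease-modifying therapy during follow-up.

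This is a weakness of description in a primary safety measure, not a bias in a planned estimate. It is worth correcting because the same SAP already adjusts relapses and TEAEs for time.

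**What to change.** In SAP 5.5.3 and Table 15.2.3, beside the raw count:

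1. Report new/enlarging T2 lesions per unit time (for example per 4 weeks or per patient-year), with the denominator taken from the actual dates of the two scans compared, including an unscheduled scan where that was the reference.
2. For Visit 7, show how many days of the interval fall before the first donation. A negative or zero value would identify a scan done on donation day.

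Contrast-enhancing lesion counts need no such rate. If the database is already locked, the SAP's introduction provides for an addendum.

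The cost is one derived variable and no new assessment, assuming that acquisition dates are held with the MRI data. With nine patients and short intervals the rates will be noisy, so the raw counts should stay in the table.
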